#### (2) Incidence of SAEs (unit: %)

**Define:** see relevant subsections of Section 12.2.1.

**Evaluation:** incidence, and relatedness of SAEs/Serious adverse device effects (SADEs) will be reported.

**Formula:** incidence of SAEs/SADEs = sum of subject who occurred SAEs/SADEs ÷ sum of subjects for each group × 100%.

**Statistical method:** The difference between investigational group the control group will be assessed.

### **(3) Incidence of Device Deficiencies (unit: %)**

**Define:** see relevant subsections of Section 12.3.1.

**Formula:** incidence of Device deficiencies = sum of subjects experienced device deficiency ÷ sum of subjects for each group × 100%.

**Statistical method:** The difference between investigational group the control group will be assessed.

## **5.4 Diagnosis and Treatment of the Investigational and Control Group**

### **5.4.1 Diagnosis and Treatment of the Investigational Group**

- Investigational device: V.A.C. VERAFLTM Dressing Kit
- Negative pressure Unit: V.A.C. ULTATM Therapy Unit (Registration No.: 国械注进 20152543887)
- Instillation solution: Normal saline
- Instructions: see the details in Instructions for Use (IFU) of V.A.C. VERAFLTM Dressing Kit (see **Appendix 3**).

**Note:** Other information for investigational device could be seen in Section 3.

### **5.4.2 Diagnosis and Treatment of the Control Group**

- Dressing Name: Negative pressure wound drainage material
- Indications: Drainage for wounds with more secretions and exudates
- Component: Negative pressure wound drainage material consists of 5 parts: sponge block, medical surgical film, drainage catheter, clamp and external fixing film of catheter pad.
- Storage  
This product is stored in a dry, light-proof and heat-proof place.
- Manufacturer: Guangdong Shuangling Pharmaceutical Co., Ltd.
- Registration No.: 国械注准 20173664628.
- Negative pressure Unit: Wall Suction.

- Instillation solution: None.
- Instructions: see the details in IFU of Negative pressure wound drainage material (see **Appendix 4**).

## **5.5 Study Procedure**

### **5.5.1 Schedule of Activities**

**Schedule of Activities**

Procedures	Screening Day -3~0	Randomization Day 0	Dressing Change Visit (s)	End of Treatment Visit 	Withdrawal or Discontinuation Visit 
Informed Consent	X				
Demographics a	X				
Medical History	X				
Surgical History	X				
Wound History b	X				
Vital Signs c	X				
Physical Exam	X	X	X	X	X
Blood Routine Examination d	X			X	X
Blood Coagulation Function e	X				
Serum Pregnancy Test f	X				
Evaluate inclusion/exclusion criteria	X	X			
Wound Clinical Assessments g		X	X	X	X
Wound Surgical Debridement		X 			
Digital/3D Wound Imaging h		X	X	X	X
Randomization		X			
NPWT		X	X		
Dressing Changes			X		
Concomitant Medications	X	X	X	X	X
AEs/SAEs Review and Evaluation	X	X	X	X	X
Device Deficiencies		X	X	X	X

**Note:**

- a:** Date of birth, Gender, Race;
- b:** Wound etiology/type, Duration, Anatomic location;
- c:** Pulse, Blood pressure, Respiration rate, Body temperature;
- d:** Red Blood Cell (RBC) count, White Blood Cell (WBC) count, Hemoglobin, Platelet;
- e:** Fibrinogen, Prothrombin Time (PT), Activated Partial Thromboplastin Time (APTT), International Normalized Ratio (INR);
- f:** Only for female subjects of reproductive potential;
- g:** Wound depth, edges, necrotic tissue type and amount, granulation tissue, undermining, exudate type and exudate amount;
- h:** Wound length, width, depth, area, and volume;

**1:** The visit will be conducted when subject is deemed ready for closure by investigator or treatment duration up to 14 Days (+/-1 Day).

**2:** For subjects withdrawing from the trial or discontinuation of trial treatment.

**3:** Definitive surgical debridement (if applicable)

## 5.5.2 Visit Time Point

### 5.5.2.1 Screening (Day-3 to 0)

The investigator will introduce the purpose of this trial and content of ICF to potential subjects. Each potential subject will review the EC approved ICF. The subject and the investigator (or designated medically licensed sub-investigator), must sign and date the ICF before the subject can undergo any clinical investigation-related procedures.

Upon signing the ICF, subjects will be assigned a unique Screening Number. The Screening Number will be a combination of the study site number (2 digits) + sequence of subject screened (3 digits begins from 001) at each site. Screened subjects will be entered onto a screening log. Once a number is assigned it cannot be re-assigned to another subject. In the instance a subject is considered a screen failure, they will keep the screening number assigned to them and the screen failure log will be completed noting the reason(s) for screen failure.

The following data will be collected:

(1) Informed consent obtained.

(2) Demographics

Date of birth, gender and race.

(3) Medical and allergic history: related to the inclusion/exclusion criteria in the past 3 months.

If the subject has diabetes history, the investigator shall evaluate whether he/she has serious diabetes (judged by investigator or fasting blood glucose level is more than 11.1mmol/L) at screening visit.

(4) Surgical history.

(5) Wound history.

The subject's wound will be assessed at screening and a wound history will be captured. The history will include prior wound related surgeries and treatments including but not limited to hyperbaric therapy, use of biologics, whirlpool, debridement, closure, revascularization procedures, prior infection, previous use

of negative pressure therapy, advanced moist wound therapy (including the solution used), which have occurred within the past 30 days. For subjects who present with multiple wounds, all wounds will be assessed at screening. The study appropriate wound with the greatest volume will be selected for the study and a wound history will be recorded.

The history will also document wound etiology/type, onset and chronicity of the wound, and anatomic location.

(6) Vital signs

Pulse, blood pressure, respiration rate, body temperature.

(7) Physical exam: Skin Assessment

A skin exam will be performed and documented as part of screening procedures. The exam should be skin focused and include observation and documentation of any pertinent findings such as skin infections (local and remote to the wound), scars (including keloids or other hypertrophic scarring), erythema/cellulitis, wounds and drainage etc.

(8) Laboratory Assessment\*

➤ Blood routine examination

Red Blood Cell (RBC) count, White Blood Cell (WBC) count, Hemoglobin, Platelet.

➤ Blood coagulation function

Fibrinogen, Prothrombin Time (PT), Activated Partial Thromboplastin Time (APTT), International Normalized Ratio (INR).

➤ Serum pregnancy test

Only for female subjects of reproductive potential.

**\*Note:** the date of laboratory assessment performed within 72 hours before screening can be collected.

(9) Evaluate inclusion/exclusion criteria.

(10) Concomitant medications

All medications the subject is taking at screening visit.

(11) Collect and assess AEs/SAEs.

### **5.5.2.2 Day of Randomization (Day 0)**

The following data will be collected:

- (1) Physical exam.
- (2) Wound clinical assessments

Wound depth, Edges, necrotic tissue type and amount, granulation tissue, undermining, exudate type and exudate amount will be evaluated.

For subjects who present with multiple wounds suitable for the trial, the wound with the greatest volume will be randomized.

- (3) Definitive surgical debridement (if applicable).
- (4) Digital/3D wound imaging

Digital photos and three-dimensional photographs will be taken of the wound (without dressing) for all subjects, and target wound length, width, depth, surface area and volume will be measured and reported.

When a wound extends over a convex/curved surface, such as a limb, the imaging will be taken so that each part of the wound is photographed (max. 2 photos) in a way that the photographed surface is as flat as possible in relation to the camera lens.

- (5) Evaluation of inclusion/exclusion criteria again.
- (6) Randomization

Subjects who continue to meet all inclusion and no exclusion criteria will be randomized in a 1:1 ratio stratified by wounds surface area (<15cm^2, 15-30cm^2, and > 30cm^2) to be treated with either investigational group [V.A.C. VERAFLTM Dressing Kit with ULTATM Therapy Unit (instillation) ] or control group [Negative pressure wound drainage material with Wall suction (without instillation)].

- (7) Administer assigned NPWT treatment

Date, time, condition and settings of NPWT treatment need to be recorded.

(8) Concomitant medications

All medications the subject is taking during the study.

(9) Collect and assess AEs/SAEs.

(10) Device deficiencies.

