#### **5.2.4 Time Point of Enrollment**

Before study specific screening assessments are performed, signed informed consent forms (ICF) must be obtained from subjects, then appropriate screening procedures will be conducted; and subjects will be taken to receive the 3D-wound imaging procedure of their wounds following the definitive surgical debridement performed (if applicable). At the end of the procedure, subjects who continue to meet all inclusion and no exclusion criteria will be included and randomized. The randomization point will be the time point of enrollment for subjects.

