### **5.5.2.4 End of Treatment Visit**

The following data will be collected before any subsequent treatment:

(1) Physical exam.

(2) Blood routine examination

RBC count, WBC count, Hemoglobin, Platelet.

(3) Wound clinical assessments.

- (4) Stop study treatment and remove NPWT dressing.
- (5) Digital/3D wound imaging (prior to commencing any subsequent treatment).
- (6) Concomitant medications

All medications the subject is taking during the study.

- (7) Collect and assess AEs/SAEs.
- (8) Device deficiencies.

**Note:** Visit will be conducted when subject's target wound is deemed ready for closure by investigator or treatment duration up to 14 Days (+/-1 Day). If the target wound can be closed judged by investigator within 14 days since initial treatment, the closure date and method are to be recorded.

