Exudate amount	1 = None, dry wound 2 = Scant, wound moist but no observable exudate 3 = Small 4 = Moderate 5 = Large	

Evaluation time point: Day of Randomization (Day 0), Dressing Change Visit (s), End of Treatment Visit.

Statistical method: The descriptive statistics (frequency and percentage) of wound clinical assessments change from baseline (change scores from -4 to +4) will be summarized by treatment group, visit and overall. Listings will be presented and sorted by treatment group, subject id.

The Wilcoxon signed rank test and the Wilcoxon rank-sum test will be performed to detect significant changes from baseline within treatment group (p-values) or significant differences in change scores between treatment groups (p-values).

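### The plan lists the only Day 0 wound clinical scores before definitive debridement and never requires them after it, so within-arm change scores could include the effect of surgery

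*Protocol*

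**What the plan says.** - **Protocol 5.5.2.2 (Day 0)** lists "2) Wound clinical assessments", then "3) Definitive surgical debridement (if applicable", then "4) Digital/3D wound imaging". The eligibility recheck, randomisation and first NPWT application follow.
- **Protocol 5.5.1 (Schedule of Activities)** keeps that sub-order in its rows: clinical assessments, "Wound Surgical Debridement", imaging. It shows one clinical assessment on Day 0 and none at screening.
- **Protocol 5.2.4** fixes the timing of imaging only: "subjects will be taken to receive the 3D-wound imaging procedure of their wounds following the definitive surgical debridement performed (if applicable". No section has a matching sentence for the 1-5 scores.
- **Protocol 5.5.2.4 (End of Treatment)** lists the clinical assessments as item 3, ahead of "4) Stop study treatment and remove NPWT dressing".
- **SAP 7.2** defines baseline by reference to the first dressing application, with no mention of debridement.
- **SAP 15.2.4** uses the signed-rank test to "detect significant changes from baseline within treatment group (p-values" and the rank-sum test to compare change scores between arms. Neither analysis takes debridement into account.

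**The concern.** The scored items include necrotic tissue type and amount, depth, edges, granulation and exudate. Several of these are what a definitive debridement alters. A site that works down the Day 0 list scores the wound, debrides it, and then images it. That score is the only one available before treatment, so it becomes the SAP baseline.

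For those subjects, necrosis removed by the surgeon would count as improvement during device treatment. Depth and granulation scores could move the other way, because debridement takes tissue out. Subjects debrided before Day 0 would have a post-debridement baseline, so baseline would not mean the same thing for everyone.

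Wound clinical assessments are named in the secondary objectives (protocol 4.2). What is at stake is the meaning of the within-arm p-values and change tables, and some precision in the between-arm test.

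**Working it through.** **Side-by-side reading.** The plan gives no figure on this point, so the first check is of the text.

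| Measure | Position in the Day 0 list | Explicit timing relative to debridement |
|---|---|---|
| 1-5 clinical scores | item 2, before debridement | none |
| 3D image (volume, area, image-based granulation) | item 4, after debridement | after it (5.2.4) |

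A pre-debridement score satisfies SAP 7.2, because it precedes the first dressing. Debridement, where done, also precedes randomisation (protocol 5.1.1, 5.2.4, 5.5.2.2). Any surgical shift is therefore expected to be equal in the two arms.

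**Inputs for an illustration of size.**
- n = 64 evaluable per arm (protocol 6.1.1). As orientation, the normal approximation gives 2 × (1.960 + 0.842)² × 0.40² ÷ 0.20² = 62.8, so 63 per arm, close to the stated 64. This concerns the primary endpoint and only sets n here.
- Share f of subjects debrided on Day 0 after scoring: **assumed**, 0 to 75%.
- Score drop from surgery: **assumed**, 1 or 2 points. On the necrosis-amount scale, 25-50% coverage scores 3. Leaving under 25% scores 2 and leaving none scores 1.
- Random change of -1, 0 or +1 with probability 0.2, 0.6 and 0.2: **assumed**.
- For power only, a device effect of a 1-point drop in 30% of the device arm: **assumed**.

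The expected shift in each arm is -f × drop; for example, 0.25 × 1 gives -0.25. The two SAP tests were run at two-sided 5% over 1,500 simulated trials per setting.

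| Drop | f | Mean change, control arm | Within-arm rejection, no device effect | Between-arm rejection, no device effect | Between-arm power |
|---|---|---|---|---|---|
| none | 0 | 0.00 | 5.0-6.0% | 4.7-4.9% | 60-61% |
| 1 | 10% | -0.10 | 18.7% | 5.1% | 54.5% |
| 1 | 25% | -0.25 | 73.4% | 3.4% | 47.5% |
| 1 | 50% | -0.50 | 99.9% | 5.3% | 45.1% |
| 1 | 75% | -0.75 | 100% | 4.7% | 47.4% |
| 2 | 10% | -0.20 | 42.6% | 4.2% | 46.1% |
| 2 | 25% | -0.50 | 97.5% | 5.6% | 31.3% |
| 2 | 50% | -0.99 | 100% | 5.1% | 24.8% |
| 2 | 75% | -1.49 | 100% | 5.1% | 31.7% |

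The within-arm test is very sensitive to even a small share of such subjects. The between-arm test keeps its error rate (3-6%) and loses power. The simulation does not bound changes by each subject's starting score, so it shows direction and order of size only.

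**The case against.** The strongest reply is that these are lists of data to collect, not timed sequences. Section 5.5.2.4 puts scoring before dressing removal, although a wound bed cannot be scored through foam. Section 5.5.2.3 puts scoring and imaging before the dressing change, although images are taken with the dressing off. The schedule places the eligibility check ahead of assessment, debridement and imaging, whereas 5.5.2.2 places the Day 0 recheck after imaging. Only the assessment-debridement-imaging sub-order agrees between the two.

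This stands as far as it goes: list position does not prove that sites scored first. But Day 0 items 3 to 7 do run in a real working order, which 5.2.4 confirms from debridement to randomisation, so a site could well read item 2 the same way. If the list is not chronological, the timing of the score is simply unspecified and sites may differ. Either reading calls for the same sentence.

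Three further points stand:
- Debridement on Day 0 is conditional, and inclusion criterion 4 describes patients already debrided. The affected share could be close to zero.
- The stated objective is the between-arm comparison, which is not biased in expectation.
- The exclusion in 5.2.2 concerns necrotic tissue with eschar, while the scoring table lists slough separately. A debrided wound need not score 1, so the size of any surgical drop is uncertain.

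**Conclusion.** The gap is real and its consequence is conditional. The only Day 0 clinical score is listed before definitive debridement, no text requires it afterwards, and the SAP baseline rule would not catch the difference. If sites score first, within-arm change in the 1-5 scores mixes surgery with treatment for subjects debrided on Day 0, and the rank-sum test gains noise.

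Four stronger readings might be inferred, and the documents do not support them:
- *That change from baseline does include surgery.* Neither the order used at sites nor the share debrided on Day 0 is stated.
- *That the comparison between arms is biased.* Debridement comes before randomisation in both arms.
- *That the primary endpoint, area or image-based granulation is contaminated.* These rest on images placed after debridement.
- *That a particular shift in mean score can be quoted.* Any such figure is an assumed share multiplied by an assumed drop, and its lower end is zero.

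The false-positive and power figures above rest on the same kind of assumption. The point warrants correction because the remedy costs almost nothing, not because a key result is in doubt.

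**What to change.** 1. **Protocol 5.5.2.2 and the Schedule of Activities:** state that the Day 0 clinical scores are taken after any definitive debridement, together with the baseline 3D image and before the first dressing. Reorder the entries to match.
2. **Protocol 5.5.2.4:** list the clinical scoring after removal of the dressing.
3. **SAP 15.2.4:** define baseline for the clinical scores as the post-debridement score.
4. **Data already collected:** establish the order of scoring and debridement from source records where possible. The plan does not require that order to be recorded, so some subjects may remain unclassified. Repeat the score analysis by Day 0 debridement status. Where baseline preceded debridement, do not present within-arm p-values as a device effect.

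SAP 15.1.4 already has a term for debridement before first application, in a sensitivity model for the primary endpoint. That term does not separate Day 0 debridement from earlier debridement, so the debridement date is needed for item 4.

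The cost is a few wording changes and one extra subgroup or sensitivity table. No procedure is added, since the wound is already exposed for imaging.

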### **5.5.2.3 Dressing Change Visits**

The following data for each dressing change visit will be collected:

(1) Physical exam.

(2) Wound clinical assessments.

(3) Digital/3D wound imaging.

(4) Dressing changes (several times)

Date and time need to be recorded.

(5) NPWT treatment

Record the condition and settings of NPWT treatment.

(6) Concomitant medications

All medications the subject is taking during the study.

(7) Collect and assess AEs/SAEs.

(8) Device deficiencies.

**Note:** The specific frequency of dressing change is determined by the investigator based on the wound condition and clinical experience while following the IFU for the assigned study product and the frequencies of the investigational and control devices are the same.

### **5.5.2.4 End of Treatment Visit**

The following data will be collected before any subsequent treatment:

(1) Physical exam.

(2) Blood routine examination

RBC count, WBC count, Hemoglobin, Platelet.

(3) Wound clinical assessments.

- (4) Stop study treatment and remove NPWT dressing.
- (5) Digital/3D wound imaging (prior to commencing any subsequent treatment).
- (6) Concomitant medications

All medications the subject is taking during the study.

- (7) Collect and assess AEs/SAEs.
- (8) Device deficiencies.

**Note:** Visit will be conducted when subject's target wound is deemed ready for closure by investigator or treatment duration up to 14 Days (+/-1 Day). If the target wound can be closed judged by investigator within 14 days since initial treatment, the closure date and method are to be recorded.

#### **5.5.2.5 Withdrawal or Discontinuation Visit**

If the subject withdraws from the trial or discontinues the trial treatment, the following data will be collected before any subsequent treatment:

- (1) Physical exam.
- (2) Blood routine examination.
- (3) Wound clinical assessments.
- (4) Digital/3D wound imaging (prior to any subsequent treatment).
- (5) Concomitant medications

All medications the subject is taking during the study.

- (6) Collect and assess AEs/SAEs.
- (7) Device deficiencies.

#### **5.5.3 Specification Direction for Use of Device**

- (1) For subjects with multiple wounds, the target wound can only be treated with the randomly assigned device and the other wounds will receive the standard wound treatment in the institution.
- (2) Placing the dressings in the target wound directly following the definitive surgical debridement (if applicable) according to the investigational or control device IFU.
- (3) During the subject's hospital admission, subjects will receive their assigned study

treatment without interruption until the wound is deemed ready for closure or up to 14 days (whichever occurred first).

- (4) For the investigational group, instillation solution (only normal saline) will be refilled by related staff as often as required. Canister changes for each group will be performed by related staff as often as required.
- (5) Dressing change frequency will be determined by the investigator based on the wound condition and clinical experience, and the frequencies of investigational and control group devices are the same (48-72h one change).
- (6) If the wound has been deemed ready for closure, study treatment will stop and subjects will then transition to receive institutional standard wound treatment at the discretion of the investigator.
- (7) If the secondary intervention condition of the target wound is not met after 14 days of treatment with the investigational device, the patient will receive further clinical treatment judged by the investigator re-evaluation according to the standard wound treatment in the institution.

#### **5.5.4 Management of Investigational Medical Device**

- (1) Investigational medical devices will be labelled and numbered uniformly and be noted “for clinical trial use only”.
- (2) Investigational medical devices will be transported to each investigational site by person designated by sponsor. The investigational sites and sponsor should establish a complete handover procedure, and the handover and receipt information including device name, model, specification, batch number and date shall be well recorded.
- (3) Each investigational site will designate a specific location for the storage of investigational device.
- (4) Each investigational site will establish strict management system for investigational device managed by designated person and create specific *Record for Use of Investigational Medical Device*. The administrator will complete the record according to the sequence of enrollment of each subject with the subject’s screen number, date of

use, device number and signature of the designated person. The administrator should record the device number on the accountability log timely and truthfully. All unused investigational V.A.C. VERAFLOT™ Dressing Kits and all V.A.C. ULTA™ Therapy Units must be returned to sponsor collectively after the completion of the trial.

